## 8.2 CLASSIFICATION OF ANAE

---

### 8.2.1 SEVERITY OF EVENT

In addition to determining whether an AE fulfils the criteria for a SAE or not, the severity of AEs experienced by study subjects will be graded according to the Common Terminology Criteria for AEs v4.03 published 14 June 2010 (CTCAE v4.03). This guidance provides a common language to describe levels of severity, to analyse and interpret data, to scale the aggregate AE score, and to articulate the clinical significance of all AEs.

The severity of AEs will be graded as follows:

Grade 1: Mild; asymptomatic or mild symptoms; clinical or diagnostic observations only; intervention not indicated.

Grade 2: Moderate; minimal, local or non-invasive intervention indicated; limiting appropriate instrumental activities of daily living.

Grade 3: Severe or medically significant but not immediately life threatening; hospitalisation or prolongation of hospitalisation indicated; disabling; limiting self activities of daily living.

Grade 4: Lifethreatening consequences; urgent intervention indicated.

Grade 5: Death related to AE.

A mild, moderate, or severe AE may or may not be serious (see Section 8.1.2). These terms are used to describe the intensity of a specific event. Medical judgment should be used on a case by case basis.

Seriousness, rather than severity assessment, determines the regulatory reporting obligations.

For guidance for assigning severity of the malaria, the purpose designed malaria clinical score will be used (Section 7.1.1).

---

## 8.2.2 RELATIONSHIP TO STUDY AGENT

The Investigator will decide if AEs are related to any of the study agents or procedures. Where possible, a distinction should be made between events considered related to the malaria challenge agent, the IMPs rescue treatments, or other protocol-mandated procedures. The assessment of causality will be made using the following definitions:

### Unrelated

This category is applicable to those AEs which are judged to be clearly and incontrovertibly due to extraneous causes (disease, environment, etc.) and do not meet the criteria for the relationship listed under unlikely, possible or probable.

### Unlikely

In general, this category is applicable to an AE which meets the following criteria (must have the first two):

1. It does not follow a reasonable temporal sequence from administration of any of the study agents.
2. It may readily have been produced by the subject's clinical state, environment or toxic factors, or other modes of therapy administered to the subject.
3. It does not follow a known pattern of response to the study agents.
4. It does not reappear or worsen when any of the study agents are administered.

### Possible

This category applies to those AEs in which the connection with any of the study agents appears unlikely but cannot be ruled out with certainty. An AE may be considered possible if or when (must have the first two):

1. It follows a reasonable temporal sequence from administration of any of the study agents.
2. It may have been produced by the subject's clinical state, environment or toxic factors, or other modes of therapy administered to the subject.
3. It follows a known pattern of response to any of the study agents.

#### Probable

This category applies to those AEs which are considered, with a high degree of certainty, to be related to the study agents. An AE may be considered probable if (must have the first three):

1. It follows a reasonable temporal sequence from administration of any of the study agents.
2. It cannot be reasonably explained by the known characteristics of the subject's clinical state, environment or toxic factors, or other modes of therapy administered to the subject.
3. It disappears or decreases on cessation or reduction in dose.
4. It follows a known pattern of response to any of the study agents.
5. It reappears on re-administration.

---

### 8.2.3 EXPECTEDNESS

An AE is regarded as unexpected even if its nature or severity is not consistent with the applicable reference safety information (S) or approved manufacturer's prescribing information for marketed drugs). Events that add significant information on the specificity, severity or frequency of previously described reactions, also regarded as unexpected.

Expected AEs from the malaria infection are listed in Appendix A and the B for the 3D7 inoculum [35]. Expected AEs from the antimalarial drugs used are listed in OZ439 IB [38] and the EMA European Public Assessment Report for PQP, Riame® Consumer Medicine Information, Primacin™ Consumer Medicine Information, and artesunate WHO Public Assessment Report 2011 (see Appendix 1).

### 8.3 TIME PERIOD AND FREQUENCY FOR EVENT ASSESSMENT AND FOLLOW-UP

All AEs must be documented and followed up by the investigator until:

- the event is resolved, or
- no further medically relevant information in relation to the event can be expected, and
- the investigator considers it justifiable to terminate the follow-up.

Events that are unresolved at the time of the subject's last follow-up visit should continue to be followed up by the investigator for as long as medically indicated. The Sponsor retains the right to request additional information for any subject with ongoing AE(s)/SAE(s) at the end of the study, if judged necessary.

All AEs should be treated appropriately. The investigator will decide upon the appropriate action to be taken in response to an AE, which may include one or more of the following:

- No action taken (i.e. further observation only).
- Dosing with the IMP is withheld and the subject withdrawn from the study.
- Administration of a concomitant medication.
- Hospitalisation or prolongation of current hospitalisation (event to be reported as an SAE).
- Other.

In a case of occurrence of SAEs, regardless of whether or not it is judged to be challenge or antimalarial drug related, the subject will receive appropriate care under clinical supervision until all the symptoms of the SAEs have diminished or resolved and the subject's condition improved.

For ongoing AEs, care will be provided for a period of time as specified in the clinical site work instruction protocols. However, if the nature of the ongoing AE is determined by the investigator as not being inoculum or antimalarial drug associated, the subject will be advised to visit his/her own general practitioner for further clinical care that he might require.

### 8.4 REPORTING PROCEDURES

#### 8.4.1 AE REPORTING

It is the investigator's responsibility to document and report all AEs occurring in the study whether spontaneously reported by the subject, observed by the investigator (either directly or by laboratory or other assessments), or elicited by general questioning. The period for collection of AEs extends from the time of inoculation up to the end of the study; these AEs must be recorded on specific AE pages of the eCRF. Events reported prior to this will be recorded as medical history, unless the symptoms worsen during the study.

The following information should be recorded for all AEs:

- Description of the AE.
- Dates and times of onset and resolution of the event.
- Duration of the event in hours.
- The time of onset relative to inoculum, or the OZ439 and PQP treatment and/or the antimalarial rescue drugs
- Seriousness of the AE (SAE or not).
- Severity of the event.
- Action taken in response to the event (including treatment required).
- Outcome of the event.
- Relationship of the event to the study agents or procedures (causality assessment), including inoculum, IMPs, rescue medication, or any other treatment or procedure conducted during the study.
- Changes in the severity of an AE will be documented to allow assessment of the duration of the event at each level of severity.
- AEs worsening in severity will be considered unresolved and those reducing in severity will be considered resolving.
- AEs characterised as intermittent require documentation of onset and duration at each episode.
- Only one AE is reported if there is a variation in intensity (with highest intensity for final CSR Tables): the description will also report the various severities over time,
- If the AE resolves and then reoccur at a later date: the AEs are reported
- All malaria-specific AEs will be tabulated and results graded according to a purpose designed malaria clinical score table (Section 7.1.1).

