### 8.1.1 DEFINITION OF AES (AE)

An AE is defined as any untoward medical occurrence, i.e., any unfavourable and unintended sign (including an abnormal laboratory finding), symptom or disease that occurs in a subject during the

course of the study and which does not necessarily have a causal relationship with this treatment (i.e., whether or not considered drug-related)

A treatment-emergent AE (TEAE) is an event that emerges following treatment with the investigational medicinal products (IMP) OZ439 and PQP, having been absent pre-treatment, or worsens relative to the pre-treatment state.

AEs include but are not limited to

- A new symptom, sign or medical condition.
- A disease or medical condition detected or diagnosed during the course of the study even though it may have been present prior to the start of the study.
- An exacerbation of a pre-existing medical condition or disease.
- An increase in frequency or intensity of a pre-existing episodic disease or medical condition.
- Continuous persistent disease symptoms present at study start that worsen following the start of the study.
- An abnormal assessment (e.g. change on physical examination, ECG findings) if it represents a clinically significant finding that was not present at study start or worsened during the course of the study.
- An abnormal laboratory test result if it represents a clinically significant finding, symptomatic or not, which was not present at study start or worsened during the course of the study or led to dose reduction, interruption or permanent discontinuation of study treatment.

Borderline abnormal laboratory findings and other objective assessments should NOT be routinely captured and reported as AEs, as they will be collected and analysed separately. However, abnormal laboratory findings or other objective measurements that meet the following criteria should be captured and reported in the AE section of the eCRF:

- the result meets the criteria for reporting as an SAE
- the test result is associated with accompanying symptoms, and/or
- it requires additional diagnostic testing or medical/surgical intervention, and/or
- it leads to a change in trial dosing, or discontinuation from the trial, significant additional concomitant drug treatment, or other therapy, and/or
- it is considered by the investigator or Sponsor to be clinically significant or represent a clinically significant change from baseline.

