#### 10.3.4 SAFETY ANALYSES

The overall number and percentage of subjects with at least one AE (and SAE) will be tabulated over the entire study period. All AE data will be summarised by pooled treatment group and study period, i.e. Day 0 to Day 8 (inoculum), Day 8 after dosing or earlier to Day 42 (OZ439 and PQP) and Day 42+2 after dosing (Rescue treatment) to (EOS visit).

Treatment emergent AE's will also be summarised with frequency counts by MedDRA system organ class (SOC; i.e. body system) and preferred term (PT), for each pooled treatment group and by Study period.

Vital signs, routine safety laboratory data and ECG parameters will be presented in data listing and will be summarised descriptively by treatment group and by protocol specified time point.

Where applicable, both absolute values and change from baseline (inoculation and IMPs administration) will be presented and listings of clinically relevant abnormal laboratory results will be generated.

The safety and tolerability of a single combined dose of OZ439 and PQP will be evaluated by the incidence, severity and relationship of observed and reported AEs up to trial Day 42.

---

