6.3 DATA HANDLING

Subject Identification Codes

For each cohort, all eligible subjects will be randomised to one of the dose groups on the morning of Day 8.

Randomisation and subject identification codes will be listed. Subject identification codes will be reported in all other listings.

Subjects who are inoculated but do not receive the IP will be included in all safety listing using their subject identification codes.

Assessment Time-Point Identifiers

In the data listings and summary tables presented as part of the CSR, scheduled assessments for Safety data will be identified by the study day name/number and/or protocol scheduled time points (Screening, Day -3 to -1, Day 0, Malaria Monitoring Visit, OZ439 and PQP treatment, and clinical unit confinement, Outpatient Monitoring, Rescue treatment with Riamet® and EOS visit and/or 4, 6, 8, 12, 24 and 72 hours post-OZ439 and PQP dosing), where relevant.

Derived Data

Derived data variables for inclusion in data listings will be calculated as follows:

- Age (in integer years) = (Screening Date – Date of Birth + 1) / 365.25)
- Body Mass Index (BMI) = Weight (kg) / (Height ² (m))
- AE time since Inoculum (in hours, to one decimal place) = (Onset Date + Onset Time) – (Inoculum Date + Inoculum Time).
- AE time since study treatment administration (in hours, to one decimal place) = (Onset Date + Onset Time) – (Study Treatment Administration Date + Study Treatment Administration Time).
- Duration of AE (in hours, to one decimal place) = (Resolution Date + Resolution Time) - (Onset Date + Onset Time).

AE time since Inoculum/study treatment administration and duration of AE will be converted to days (to one decimal place) in the follow-up period.

Handling of Missing Data

Missing values will not be imputed and will be reported in the listings as either “missing” or as the justification for the value being missing e.g. “ND” (not detected), where appropriate.

	STATISTICAL ANALYSIS PLAN	QP17C19
		Page 19 of 53

For the current study the duration of historical medical conditions and prior and concomitant medication administration will not be calculated or summarised and as such missing start and end times/dates will not be imputed.

Descriptive statistics will be calculated from actual data only, with the number of actual data points used for the calculation of the summary statistics reported. Missing data will not be imputed.

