6.8 SAFETY DATA

Adverse events

Adverse events (AEs) and AESIs will be coded using the most current Medical Dictionary for Regulatory Activities (MedDRA®) available at CNS (21.0). Listings of AEs, as well as the severity, relationship, duration, outcome, actions taken, and whether the AE was treatment-emergent and/or an SAE will be presented for each subject. Treatment-emergent adverse events (TEAEs) will be defined as any AE with an onset after administration of study drug, or any AE that has worsened after administration of study drug.

An AESI (serious or non-serious) is one of scientific and medical concern specific to the Sponsor's product or programme, for which ongoing monitoring and rapid communication by the Investigator to the Sponsor could be appropriate. Any abnormalities listed below should be reported as AESI:

Hepatic:

- any ALT or AST above 5xULN
- an elevation in bilirubin 2xULN
- any AST or ALT above 2xULN and (TBL > 1.5x ULN or INR > 1.4)
- any AST or ALT above 2xULN with the appearance of fatigue, nausea, vomiting, right upper quadrant pain or tenderness, fever, rash and/or eosinophilia (eosinophil percent or count above the ULN)

	
STATISTICAL ANALYSIS PLAN
	
QP17C19

		
Page 21 of 53

Cardiac:

- QTcB or QTcF at any time >480 msec,
- bundle branch block (except right bundle branch block that was present prior to IP administration)

any arrhythmia, except:

- sinus bradycardia that is
 - clinically asymptomatic, and
 - not associated with any other relevant ECG abnormalities
- sinus tachycardia that is
 - clinically asymptomatic, and
 - associated with a body temperature >38.0 °C, and
 - not associated with any other relevant ECG abnormalities

respiratory sinus arrhythmia,

wandering atrial pacemaker,

isolated, single premature atrial/ventricular complex (i.e. no bigeminy, trigeminy, couplets, triplets or salvos) that does not occur more than once in a particular ECG tracing.

Haematological:

HB drop >2.0 g/dL from baseline prior to inoculation

Absolute neutrophil count <500/µl.

Platelet count <75,000 /mm³

Dermatological:

Clinical signs of possible cutaneous adverse reactions such as:

- dermatitis,
- rash,
- erythematous rash,
- macular rash,
- papular rash,
- maculopapular rash,
- pruritic rash,
- pustular rash,
- vesicular rash.

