14.3 Safety Data			
	Table14.3.1.1a	Overall Summary of Inoculum-Emergent Adverse Events	Inoculum
	Table14.3.1.1b	Overall Summary of Treatment-Emergent Adverse Events	Safety
	Table14.3.1.2a	Inoculum-Emergent Adverse Events by MedDRA System Organ Class and Preferred Term	Inoculum

	STATISTICAL ANALYSIS PLAN	QP17C19
		Page 50 of 53

Table Number	Table Title	Population
Table 14.3.1.2b	Treatment-Emergent Adverse Events by MedDRA System Organ Class and Preferred Term	Safety
Table 14.3.1.3a	Inoculum-Related Inoculum-Emergent Adverse Events by MedDRA System Organ Class and Preferred Term	Inoculum
Table 14.3.1.3b	IMP-Related Treatment-Emergent Adverse Events by MedDRA System Organ Class and Preferred Term	Safety
Table 14.3.1.4a	Inoculum-Emergent Adverse Events by MedDRA System Organ Class, Preferred Term and Maximum Severity	Inoculum
Table 14.3.1.4b	Treatment-Emergent Adverse Events by MedDRA System Organ Class, Preferred Term and Maximum Severity	Safety
Table 14.3.1.5a	Overall Summary of Inoculum-Emergent AESIs	Inoculum
Table 14.3.1.5b	Overall Summary of Treatment-Emergent AESIs	Safety
Table 14.3.1.6a	Inoculum-Emergent Adverse Events by MedDRA Preferred Term	Inoculum
Table 14.3.1.6b	Treatment-Emergent Adverse Events by MedDRA Preferred Term	Safety
Table 14.3.2a	Malaria Clinical Score and Change from Baseline	Inoculum
Table 14.3.2b	Malaria Clinical Score and Change from Baseline	Safety

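### One AE record at its highest grade, with no split at OZ439/PQP or at Riamet, can misstate grade and phase for AEs that straddle dosing or rescue

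*Protocol*

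**What the plan says.** **Recording.** Protocol 8.4.1 sets the rule: "Only one AE is reported if there is a variation in intensity (with highest intensity for final CSR Tables". A worsening AE stays open as unresolved. The same section protects the detail: "Changes in the severity of an AE will be documented to allow assessment of the duration of the event at each level of severity", and "the description will also report the various severities over time". An AE that resolves and later returns is handled separately.

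**Treatment emergence.** Protocol 8.1.1 counts an event that follows OZ439/PQP, "having been absent pre-treatment, or worsens relative to the pre-treatment state". SAP 6.8 uses "any AE with an onset after administration of study drug, or any AE that has worsened after administration of study drug". Neither definition mentions rescue medication.

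**Period and phase.** Protocol 10.3.4: "All AE data will be summarised by pooled treatment group and study period", with inoculum, OZ439/PQP and rescue periods. SAP 6.8 has two AE phases, treatment and rescue, and tabulates TEAEs by phase and overall.

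**Timing.** SAP 6.3 derives "AE time since study treatment administration (in hours, to one decimal place") as onset minus dosing time, for the listings. No time of worsening is derived.

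**Severity tables.** SAP Appendix 2 plans Table 14.3.1.4b, "Treatment-Emergent Adverse Events by MedDRA System Organ Class, Preferred Term and Maximum Severity", on the safety set, and a matching Table 14.3.1.4a for inoculum-emergent AEs. The SAP does not define *inoculum-emergent*. It also does not say whether maximum severity is taken over the whole record or within a phase.

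**The concern.** Every subject is inoculated about 8 days before receiving OZ439/PQP, so an AE may already be open at dosing. Headache, nausea, vomiting and abdominal discomfort are items of the malaria clinical score (Protocol 7.1.1). Headache, nausea, vomiting and abdominal pain are also among the AEs described for OZ439 (Protocol 2.3.1). For these terms, separating malaria from drug effect depends on what changed after dosing.

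The same situation is foreseeable at rescue. The Cohort 1 doses were chosen so that parasite regrowth could be seen (Protocol 2.2). Recrudescence, including a clinical score above 6, is a ground for early Riamet (Protocol 7.3.3). Some subjects may therefore have symptoms open when Riamet starts.

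The primary safety endpoint is the incidence, severity and relationship of AEs to OZ439 and PQP. If the grade and phase of a straddling AE are not governed by a stated rule, the tables that describe this endpoint rest on choices left to the programmer.

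**Working it through.** The plan gives no figure to reproduce on this point. The check has three parts.

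**1. Grade across dosing.** Take one AE that opens before dosing, is still open at dosing and gets worse afterwards. Let P be its peak grade before dosing, D its grade at dosing (D ≤ P) and Q its peak grade after dosing (Q > D). Under 8.4.1 the tabulated grade is max(P, Q). The correct TEAE grade is Q. The correct grade for a summary limited to pre-dose time is P. With grades 1 to 3:

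| P | D | Q | Tabulated | TEAE grade | Pre-dose grade |
|---|---|---|---|---|---|
| 1 | 1 | 2 | 2 | right | too high |
| 1 | 1 | 3 | 3 | right | too high |
| 2 | 1 | 2 | 2 | right | right |
| 2 | 1 | 3 | 3 | right | too high |
| 2 | 2 | 3 | 3 | right | too high |
| 3 | 1 | 2 | 3 | too high | right |
| 3 | 1 | 3 | 3 | right | right |
| 3 | 2 | 3 | 3 | right | right |

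- Simple worsening (D = P, 3 patterns): the TEAE grade is right in 3 of 3; the pre-dose grade is too high in 3 of 3.
- All 8 patterns: the TEAE grade is wrong in 1 (grade 3, then 1, then 2); the pre-dose grade is wrong in 4.
- These are counts of patterns, not probabilities.

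The table takes worsening relative to the grade at dosing, which the documents do not specify. If it were judged against the pre-dose peak instead (Q > P), only 4 of the 8 patterns (1-1-2, 1-1-3, 2-1-3, 2-2-3) would be TEAEs, and all 4 would have the right TEAE grade. The other 4 would lose the TEAE flag. The choice of reference grade therefore decides the count as well as the grade.

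**2. Phase at rescue.** Take an AE that begins at grade 1 after OZ439/PQP and reaches grade 3 after Riamet. It is one record with a treatment-phase onset and a single grade of 3. The worsening limb of the TEAE definition refers to study drug, and nothing equivalent exists for Riamet. No rule brings the worsening into the rescue phase, and none keeps the grade 3 out of a treatment-phase summary.

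**3. Size of one wrong cell.** SAP Section 5 summarises by dose group unless otherwise specified, and SAP 2.1 gives groups of 2 (Cohort 1) and 4 (Cohorts 2 and 3). One subject is 100/2 = 50 points, 100/4 = 25 points, or 100/24 = 4.2 points over all subjects. The documents do not say how many AEs straddle dosing or rescue, so no expected error can be computed.

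**The case against.** The case against is substantial, and much of it stands.

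- **The ordinary case is handled.** A symptom that simply worsens after dosing is caught by both TEAE definitions, and its highest grade is the correct post-dose grade. This stands.
- **Placing a post-drug grade in Day 0 to 8 is not prescribed.** A reader might infer that straddling AEs are allocated by onset. Neither Protocol 10.3.4 nor SAP 6.8 says so. The SAP prevails where its analyses differ, and its phases are treatment and rescue only. If inoculum-emergent means any time from inoculation onward, the later grade belongs in Table 14.3.1.4a. The pre-dose error arises only if that summary stops at dosing, and the missing definition leaves this open.
- **Onset is not wrong.** A negative time since treatment is correct for an AE that began before dosing, and the variable feeds listings. What is missing is a time of worsening.
- **The malaria clinical score covers the same symptoms.** It is graded at admission and three times daily in confinement, and the SAP tabulates each symptom by treatment and time point. This helps around dosing. After discharge the score is taken only if vital signs are abnormal or at the Investigator's discretion, so cover is thinner up to rescue. It also uses its own 0 to 3 scale, not the CTCAE grades of the AE tables.
- **Causality tables also separate the sources.** SAP 6.8 plans separate tables for TEAEs related to inoculum, treatment and rescue drug. However, a single record holds one assessment per agent, and 8.4.1 does not ask for a new one when the AE worsens.
- **No data are lost.** Severity changes are documented, and listings for 24 subjects can be read individually. This makes the gap cheap to close, but it does not supply the rule.

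**Conclusion.** The point holds as a limited analysis defect. The recording rule gives one grade per AE, while the plan asks for summaries by phase and by emergence type. As written, three things follow:

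- A pre-dose peak can appear as the TEAE grade when it exceeds the post-dose peak, provided worsening is judged from the grade at dosing.
- An inoculum summary limited to pre-dose time would show a post-drug grade.
- Worsening after Riamet has no stated route into the rescue phase. This is the clearest gap.

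A reader might go further and infer that the primary safety endpoint is biased. The documents do not support that. The endpoint is descriptive, Protocol 4.2.1 sets it up to Day 42±2 without a period split, simple worsening is graded correctly, and neither the frequency nor the direction of error can be derived. The 50- and 25-point shifts are what any one-subject error would produce in groups this small; they do not estimate bias. Bias is possible but not shown.

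**What to change.** Amend SAP 6.3 and 6.8, and align Protocol 8.4.1 so that the highest intensity used in tables is the highest within phase:

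1. Define *inoculum-emergent*, including whether it ends at the first OZ439/PQP dose.
2. Judge worsening against the grade at the first OZ439/PQP dose and, for the rescue phase, at the first Riamet dose. Anchor the rescue phase at that dose too: the SAP ties it to Day 42±2, although Riamet may start earlier.
3. Derive the date and time of worsening from the severity changes that 8.4.1 already requires.
4. Count a worsened AE in the phase in which it worsened; the earlier part keeps its own phase.
5. Use the maximum grade within the phase, not over the whole record, in the severity tables.
6. Where feasible, record causality for the worsening separately.

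The cost is SAP wording and one derivation before database lock, with an eCRF completion note if causality is recorded separately. A straddling event will appear in two phases, so event counts by phase rise slightly. Severities held only as free text will need coding.
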